## 5.2. INCLUSION CRITERIA

Subjects will be considered qualified for enrollment if they meet the following criteria:

1. Legally authorized representative of subjects willing and able to give consent. Assent will be obtained for subjects between the ages of 7 and 10 years old.
2. Subjects will need to be 6 months of age to 10 years of age at the time of entry into the study.
3. The minimum weight of a subject will need to be 8 kg at the time of enrollment.
4. Subjects will be required to have the clinical diagnosis of lymphatic malformation that appears to be over 3 cm in greatest diameter in order to be evaluated for entry. A review of a previous MRI examination may help confirm the entry criteria on subjects selected to come to Stanford for the MRI screening. The MRI must be performed within six (6) months of the screening visit if used as a baseline measure.
5. The lymphatic malformation should be causing enough disability for the subject requiring them to consider systemic therapy.
6. Females must not be pregnant or breast-feeding.
7. Female subjects of childbearing potential have negative urine-pregnancy test results.
8. A parent or legally authorized representative must be willing and able to ensure subject is present for all required study visits.
9. A parent or legally authorized representative must be able to follow instructions.
10. During the initial screening evaluation portion of the trial the subjects MRI examination will be required to confirm that the lymphatic malformation is present and is greater than 3 cm in diameter in order for the subjects to receive medication. MRI of less than six months is valid to use during screening with the discretion of the study radiologist.
11. Subjects will have no contraindications for the use of sildenafil.
12. Subjects will have a normal eye examination.
13. Subjects will have normal liver and kidney function.
14. Subjects will have no contraindication to MRI examinations such as metal implants, etc.
15. Subject must not be a smoker.

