### 5.3. EXCLUSION CRITERIA

A participant will be ineligible if he/she meets any of the following criteria:

1. The participant has a medically unstable health status that may interfere with his/her ability to complete the study.
2. The participant presents with one or more of the following medical conditions: Hepatic impairment, severe renal impairment, lymphedema conditions such as Milroy disease, Meige lymphedema, Hennekam syndrome, Njolstad syndrome, Aagenaes syndrome, and Fabry disease, hypotension or at risk for hypotension, seizures or history of seizures, any significant cardiovascular risk factors and any condition which requires participants to use nitric oxide donors or nitrates in any form, underlying anatomic or vascular risk factor for developing non-arteritic anterior ischemic optic neuropathy (NAION) including low ocular cup to disc ratio, diabetes, hypertension, coronary artery disease, or hyperlipidemia. Participants with Down syndrome, Turner syndrome and Noonan syndrome will be considered on a case-by-case basis.
3. The participant has received at least one of the following medications contraindicated in association with sildenafil within 15 days of inclusion:
  - Organic nitrates in any form, either regularly or intermittently -- Consistent with its known effects on the nitric oxide/cGMP pathway, sildenafil was shown to potentiate the hypotensive effects of nitrates.
  - Ritonavir and other Potent CYP3A Inhibitors --- Concomitant use of REVATIO with ritonavir and other potent CYP3A inhibitors is not recommended.
  - Alpha-blockers --- co-administering alpha-blockers with REVATIO because of additive blood pressure-lowering effects
  - Amlodipine
  - Cimetidine
4. The participant requires concomitant use of potent cytochrome P450 3A4 inhibitors (such as ketoconazole, itraconazole, erythromycin, saquinavir), or concomitant use of ritonavir. Also excluded are concomitant use of organic nitrates, alpha-blockers, amlodipine, or cimetidine.
5. The screening MRI cannot confirm that the lesion is a lymphatic malformation or the lymphatic malformation is less than 3 cm in its greatest diameter.
6. The patient has had extensive prior surgery or sclerotherapy to treat LM such that scarring may interfere with evaluation and treatment effect of sildenafil.

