### 17.2 INSTRUCTIONS OF ORAL SUSPENSION FOR PHARMACIST

### 17.2.1 Instructions for Pharmacist (2 pages)

page 1:

|   |
|---|
| 
INSTRUCTIONS FOR PHARMACIST FOR
COMPOUNDING REVATIO® 20MG TABLETS
 
Compounding of an extemporaneously prepared oral suspension from <del>Revatio®</del> 20 mg film-coated tablets (final concentration 10 mg/ml). Compounding of an oral suspension, by a pharmacist, following this procedure, will provide one patient with enough medicinal product for a: 28-day course of treatment (1 ml dosing volume, 10 mg dose) or a 14-day course of treatment (2 ml dosing volume, 20 mg dose).
 
Ingredients:
 
The compounding of the <del>Revatio®</del> oral suspension from <del>Revatio®</del> 20 mg tablets uses <del>Ora-Sweet</del> and <del>Ora-Plus</del> diluents.
 
Compounding instructions for a pharmacist:
 

1. Ensure <del>Ora-Sweet</del> and <del>Ora-Plus</del> have been equilibrated to room temperature.

2. Count 62 (sixty two) x 20 mg <del>Revatio</del> tablets.

3. Using a mortar and pestle, crush these 62 tablets, 2-10 tablets at a time, into a fine powder.

4. Measure out 30 ml <del>Ora-Plus</del> (cloudy white liquid), allowing time for any air bubbles to dissipate.

5. Add a portion (15-20 ml typical) of <del>Ora-Plus</del> from step 4 to the mortar and mix into a thick homogeneous paste. More <del>Ora-Plus</del> from step 4 may be added if necessary.

6. Transfer the paste to an amber glass or <del>high density</del> polyethylene (HDPE) bottle (<math>\geq</math> 150 ml volume)

7. Rinse the mortar and pestle with the remaining <del>Ora-Plus</del> from step 4 and transfer <del>rinses</del> to the bottle to ensure complete transfer of the paste.

8. Measure 90 ml <del>Ora-Sweet</del> (clear pink liquid) allowing time for any air bubbles to dissipate.

9. Transfer approximately half of the volume of the <del>Ora-Sweet</del> from step 8 to the bottle containing the formulation prepared above.

10. Cap bottle and shake vigorously for a minimum of 30 seconds.

11. Transfer the remaining <del>Ora-Sweet</del> from step 8 to the bottle and shake vigorously

 |
|---|

page 2:

INSTRUCTIONS FOR PHARMACIST FOR

COMPOUNDING REVATIO® 20MG TABLETS

again for a minimum of 30 seconds to achieve a homogenous oral suspension.

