12. Put an ancillary label on the bottle warning "Patients with rare hereditary problems of fructose intolerance, glucose-galactose malabsorption or sucrase-isomaltase insufficiency, should not take this medicinal product". The ancillary label should also indicate "Shake well for a minimum of 10 seconds before each dosing". Include the patient's name, dosing instructions, expiry date, and medicinal product name.

13. Instruct the person who is to administer the compounded product that any remaining material following completion of therapy must be discarded by either affixing an ancillary label to the bottle or adding a statement to the pharmacy label instructions.

14. Place an appropriate expiration date label according to storage condition.

Consider dispensing the oral suspension with an appropriate graduated oral dosing syringe for measuring the required volumes of oral suspension.

If possible, mark or highlight the graduation corresponding to the appropriate dose (1 ml or 2 ml) on the oral dosing syringe for each patient.

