### 17.2.2 Pharmacist Instructions for Oral Suspension of 10mg and 20mg

Subjects taking 20mg/8ml

| LYMPHATIC MALFORMATION STUDY   |          |          |          |                     |
|--|----------|----------|----------|---------------------|
| Sildenafil 2.5mg/ml or Placebo suspension   |          |          |          |                     |
| COMPOUNDING FORMULA  |          |          |          |                     |
|  | Lot#     | Exp Date | Rph1     | RPh2                |
| Sildenafil 20mg or Placebo   | 105 tabs |          |          |                     |
| OraSweet   | 420ml    |          |          |                     |
| OraPlus  | 420ml    |          |          |                     |
| **Use Study Sildenafil or Placebo tablet provided by Pfizer**  |          |          |          |                     |
| Date   | Cpd by   | Chk by   | Exp Date | Appearance/Comments |
| Equipment: mortar and pestle, graduated cylinder, stirring rod   |          |          |          |                     |
| Preparation:  |          |          |          |                     |
| 1-Count out 105 tablets of Sildenafil or Placebo.  |          |          |          |                     |
| 2-Grind tablets in a mortar with a pestle, and triturate to a fine powder.   |          |          |          |                     |
| 3-Mix 420ml of OraSweet with 420ml OraPlus. Use mixture as base solution.  |          |          |          |                     |
| 4-Levigate with a small amount of base solution to form a uniform paste.   |          |          |          |                     |
| 5-Add base solution in geometric proportions almost to 840ml, while mixing thoroughly.   |          |          |          |                     |
| 6-Transfer contents of the mortar to a graduated cylinder.   |          |          |          |                     |
| 7-Rinse the mortar and pestle with base solution and pour into graduated cylinder.   |          |          |          |                     |
| 8-Add base solution to the graduated cylinder to achieve the total volume of 840ml.  |          |          |          |                     |
| 9-Transfer contents of the graduated cylinder into bottles provided by the study.  |          |          |          |                     |
| 10-Shake well to mix   |          |          |          |                     |

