| Beyond Use Date: 91 days  |          |          |          |                     |
| Storage: Refrigerate  |          |          |          |                     |
| Reference: Milap C. Nabata, Richard S. Morasco, and Michael T. Brady. Extemporaneous sildenafil citrate oral suspensions for the treatment of pulmonary hypertension in children. American Journal of Health-System Pharmacy, Vol.63, Issue 3, 254-257 |          |          |          |                     |

Subjects taking 10mg/4ml

| LYMPHATIC MALFORMATION STUDY   |         |          |          |                     |
|--|---------|----------|----------|---------------------|
| Sildenafil 2.5mg/ml or Placebo suspension   |         |          |          |                     |
| COMPOUNDING FORMULA  |         |          |          |                     |
|  | Lot#    | Exp Date | Rph1     | RPh2                |
| Sildenafil 20mg or Placebo   | 60 tabs |          |          |                     |
| OraSweet   | 240ml   |          |          |                     |
| OraPlus  | 240ml   |          |          |                     |
| **Use Study Sildenafil or Placebo tablet provided by Pfizer**  |         |          |          |                     |
| Date   | Cpd by  | Chk by   | Exp Date | Appearance/Comments |
| Equipment: mortar and pestle, graduated cylinder, stirring rod   |         |          |          |                     |
| Preparation:   |         |          |          |                     |
| 1-Count out 60 tablets of Sildenafil or Placebo.   |         |          |          |                     |
| 2-Grind tablets in a mortar with a pestle, and triturate to a fine powder.   |         |          |          |                     |
| 3-Mix 240ml of OraSweet with 240ml OraPlus. Use mixture as base solution.  |         |          |          |                     |
| 4-Levigate with a small amount of base solution to form a uniform paste.   |         |          |          |                     |
| 5-Add base solution in geometric proportions almost to 480ml, while mixing thoroughly.   |         |          |          |                     |
| 6-Transfer contents of the mortar to a graduated cylinder.   |         |          |          |                     |
| 7-Rinse the mortar and pestle with base solution and pour into graduated cylinder.   |         |          |          |                     |

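### The 17.2.1 label carries a warning on three hereditary sugar disorders and a shake-before-dosing instruction; the 2.5 mg/ml sheets in 17.2.2 carry neither, and no entry criterion or screening step names the disorders

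*Combined protocol and SAP*

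**What the plan says.** Section 17.2.1 describes a suspension made from 20 mg Revatio tablets in Ora-Plus and Ora-Sweet ("final concentration 10 mg/ml"), dosed as 1 ml or 2 ml. Step 12 orders an ancillary label stating "Patients with rare hereditary problems of fructose intolerance, glucose-galactose malabsorption or sucrase-isomaltase insufficiency, should not take this medicinal product" and also "Shake well for a minimum of 10 seconds before each dosing".

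The Synopsis and Section 4.2 describe a different strength, 2.5 mg/ml, dosed as 4 ml or 8 ml. The two sheets in 17.2.2 make that strength from sildenafil or placebo tablets. For the 20 mg dose the sheet reads "3-Mix 420ml of OraSweet with 420ml OraPlus. Use mixture as base solution"; for the 10 mg dose, "3-Mix 240ml of OraSweet with 240ml OraPlus. Use mixture as base solution". Each ends with the pharmacist shaking the mixture, a beyond-use date and a storage line. Neither has a labelling step.

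On entry, exclusion item 2 in 5.3 opens "The participant presents with one or more of the following medical conditions: Hepatic impairment, severe renal impairment, lymphedema conditions" and continues through a list that contains none of the three disorders. Inclusion item 11 in 5.2 reads "Subjects will have no contraindications for the use of sildenafil". Exclusion item 9 concerns allergy to sildenafil, and item 14 lets the investigator exclude a subject on medical grounds. Sections 7.1.2 and 7.1.3 take a medical history without naming these disorders. Section 4.2 asks for suitable cautionary text on every bottle, unspecified.

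The Synopsis and 4.2 let the family choose tablets or suspension. Section 7.1.3, step 10, says that subjects will be given the suspension.

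**The concern.** The plan's own label says that children with any of three conditions should not take a suspension made from these tablets and these diluents. The sheets that match the trial's stated strength and dose volumes do not repeat this, and nothing in the eligibility list or the screening steps prompts anyone to ask. Under 6.1, randomisation follows the screening tests; under 7.1.3, the first dose is taken in clinic on Day 0. A statement that exists only on a bottle label is therefore met after allocation. At stake is an avoidable exposure in a paediatric trial.

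The shake instruction raises a separate, smaller point. A suspension that the family does not shake may deliver an uneven dose through the bottle, and 17.2.1 is the only place that tells the family to shake it.

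**Working it through.** **Which sheet makes the study suspension.** Concentration = tablets × 20 mg ÷ volume.
- 17.2.2, 20 mg sheet: 105 × 20 ÷ 840 = 2.5 mg/ml, as stated.
- 17.2.2, 10 mg sheet: 60 × 20 ÷ 480 = 2.5 mg/ml, as stated.
- 17.2.1: 62 × 20 ÷ (90 + 30) = 10.3 mg/ml, against a stated 10 mg/ml. The volume here counts the diluents only.

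The 17.2.2 sheets reproduce the strength in the Synopsis and 4.2; 17.2.1 does not. Nothing marks 17.2.1 as superseded, and the cross-references do not settle the matter. Section 4.3 sends the reader to 17.1 for compounding, which is the laboratory list; 7.1.3, step 10, sends the reader to a Section 18.2 that does not exist.

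**The passages side by side.**

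| Item | 17.2.1 | 17.2.2 (both sheets) |
|---|---|---|
| Tablets | Revatio 20 mg | Sildenafil 20 mg or placebo |
| Diluents | Ora-Plus 30 ml, Ora-Sweet 90 ml | OraPlus and OraSweet in equal volumes |
| Warning on three disorders | Yes, step 12 | None |
| Shake-before-dosing label | Yes, step 12 | None (shaking is a pharmacist step) |

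**Eligibility.** Criteria naming any of the three disorders: 0 of 15 inclusion and 0 of 15 exclusion. Screening or Day 0 steps naming them: none. Inclusion 11 and exclusion 9 speak of sildenafil, not of the compounded product. Exclusion 14 is discretionary. The medical history could bring the diagnosis to light, but no criterion says what follows from it.

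**Can exposure be sized?** Only by assuming which ingredient prompts the warning, because the documents do not say. Amount per 10 mg dose = share of volume × dose volume:
- If Ora-Sweet: 17.2.1 gives 90/120 × 1 ml = 0.75 ml; 17.2.2 gives 240/480 × 4 ml = 2.0 ml; ratio 2.0/0.75 = 2.7.
- If Ora-Plus ("Measure out 30 ml" in 17.2.1): 30/120 × 1 ml = 0.25 ml against 240/480 × 4 ml = 2.0 ml; ratio 8.
- If the tablet: 10.3 mg against 10 mg of tablet strength, i.e. about half a tablet either way; ratio about 1.

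The ratio thus runs from about 1 to 8 according to an assumption that the documents leave open. No single figure should be carried forward.

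**The case against.** The strongest reply has four parts.

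First, general safeguards exist. Inclusion 11 could be read to bar such a child, exclusion 14 lets the investigator do so, prescreening under 7.1.1 seeks medical records, and a history is taken twice. This stands to the extent that a reader might infer that the criteria positively admit these children, and the documents do not support that. What they show is that no criterion names the disorders and that only general clauses could catch them.

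Second, the 17.2.2 pages are compounding worksheets, and 4.2 separately requires cautionary text on each bottle. So absence from the worksheet does not prove absence from the bottle. This also stands in part. But 4.2 does not say which cautions, and if 17.2.1 were withdrawn the specific warning and the shake instruction would have no source left in the protocol. The handout given to families under 7.1.3, step 12, is not available to check.

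Third, tablets are offered in the Synopsis and 4.2, so a child for whom the suspension is unsuitable need not be excluded. That is fair, and it means the documents do not establish that exclusion is the answer. It does not close the gap, because 7.1.3, step 10, says that the suspension is given and nothing links the choice of form to these disorders.

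Fourth, a reader might infer that the 20-week MRI would be lost for a child recognised late. The documents do not establish this. Nothing says that such a child exits. On early exit the plan also disagrees with itself: footnote 5 to Table 16-1 says there is no final MRI, while 7.1.13 and 7.2 call for the end-of-treatment procedures.

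**Conclusion.** The inconsistency is real and small. A pharmacist who follows 17.2.2 as written omits a safety warning and a shake-before-dosing instruction that 17.2.1 requires for the same sildenafil tablets and diluents. Nothing specific in the entry criteria or screening makes up for the missing warning.

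Two stronger readings go too far. One is that the study suspension gives 2.7 times the relevant exposure; that holds only if Ora-Sweet prompts the warning. The other is that both arms are affected. Both arms share the diluents, but the content of the placebo tablets is not described, so this holds only if a diluent is the cause.

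The probability that any enrolled child is affected is low: the label calls the conditions rare, the documents give no prevalence, and planned enrolment is about 60. The case for correcting it rests on an avoidable risk to a child and a very small cost, not on any effect on the efficacy analysis.

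**What to change.** The sponsor's pharmacist and medical lead should reconcile 5.2 and 5.3, step 12 of 17.2.1, both 17.2.2 sheets, and the statements on tablets versus suspension (Synopsis and 4.2 against 7.1.3, step 10). The amendment should:

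1. State whether the warning in step 12 applies to the 2.5 mg/ml study suspension, and on account of which ingredient.
2. Make the warning and the shake-before-dosing label consistent across 17.2.1 and both 17.2.2 sheets. Each 17.2.2 sheet serves active and placebo alike, so wording placed there will not distinguish the arms.
3. If the warning applies, make sure the point is checked before randomisation.

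How such a child is then handled, including any choice between formulations, is for the sponsor to decide. The cost is a few lines in a protocol amendment.

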### 17.2.2 Pharmacist Instructions for Oral Suspension of 10mg and 20mg

Subjects taking 20mg/8ml

| LYMPHATIC MALFORMATION STUDY   |          |          |          |                     |
|--|----------|----------|----------|---------------------|
| Sildenafil 2.5mg/ml or Placebo suspension   |          |          |          |                     |
| COMPOUNDING FORMULA  |          |          |          |                     |
|  | Lot#     | Exp Date | Rph1     | RPh2                |
| Sildenafil 20mg or Placebo   | 105 tabs |          |          |                     |
| OraSweet   | 420ml    |          |          |                     |
| OraPlus  | 420ml    |          |          |                     |
| **Use Study Sildenafil or Placebo tablet provided by Pfizer**  |          |          |          |                     |
| Date   | Cpd by   | Chk by   | Exp Date | Appearance/Comments |
| Equipment: mortar and pestle, graduated cylinder, stirring rod   |          |          |          |                     |
| Preparation:  |          |          |          |                     |
| 1-Count out 105 tablets of Sildenafil or Placebo.  |          |          |          |                     |
| 2-Grind tablets in a mortar with a pestle, and triturate to a fine powder.   |          |          |          |                     |
| 3-Mix 420ml of OraSweet with 420ml OraPlus. Use mixture as base solution.  |          |          |          |                     |
| 4-Levigate with a small amount of base solution to form a uniform paste.   |          |          |          |                     |
| 5-Add base solution in geometric proportions almost to 840ml, while mixing thoroughly.   |          |          |          |                     |
| 6-Transfer contents of the mortar to a graduated cylinder.   |          |          |          |                     |
| 7-Rinse the mortar and pestle with base solution and pour into graduated cylinder.   |          |          |          |                     |
| 8-Add base solution to the graduated cylinder to achieve the total volume of 840ml.  |          |          |          |                     |
| 9-Transfer contents of the graduated cylinder into bottles provided by the study.  |          |          |          |                     |
| 10-Shake well to mix   |          |          |          |                     |
| Beyond Use Date: 91 days  |          |          |          |                     |
| Storage: Refrigerate  |          |          |          |                     |
| Reference: Milap C. Nabata, Richard S. Morasco, and Michael T. Brady. Extemporaneous sildenafil citrate oral suspensions for the treatment of pulmonary hypertension in children. American Journal of Health-System Pharmacy, Vol.63, Issue 3, 254-257 |          |          |          |                     |

Subjects taking 10mg/4ml

| LYMPHATIC MALFORMATION STUDY   |         |          |          |                     |
|--|---------|----------|----------|---------------------|
| Sildenafil 2.5mg/ml or Placebo suspension   |         |          |          |                     |
| COMPOUNDING FORMULA  |         |          |          |                     |
|  | Lot#    | Exp Date | Rph1     | RPh2                |
| Sildenafil 20mg or Placebo   | 60 tabs |          |          |                     |
| OraSweet   | 240ml   |          |          |                     |
| OraPlus  | 240ml   |          |          |                     |
| **Use Study Sildenafil or Placebo tablet provided by Pfizer**  |         |          |          |                     |
| Date   | Cpd by  | Chk by   | Exp Date | Appearance/Comments |
| Equipment: mortar and pestle, graduated cylinder, stirring rod   |         |          |          |                     |
| Preparation:   |         |          |          |                     |
| 1-Count out 60 tablets of Sildenafil or Placebo.   |         |          |          |                     |
| 2-Grind tablets in a mortar with a pestle, and triturate to a fine powder.   |         |          |          |                     |
| 3-Mix 240ml of OraSweet with 240ml OraPlus. Use mixture as base solution.  |         |          |          |                     |
| 4-Levigate with a small amount of base solution to form a uniform paste.   |         |          |          |                     |
| 5-Add base solution in geometric proportions almost to 480ml, while mixing thoroughly.   |         |          |          |                     |
| 6-Transfer contents of the mortar to a graduated cylinder.   |         |          |          |                     |
| 7-Rinse the mortar and pestle with base solution and pour into graduated cylinder.   |         |          |          |                     |
| 8-Add base solution to the graduated cylinder to achieve the total volume of 480ml.  |         |          |          |                     |
| 9-Transfer contents of the graduated cylinder into bottle provided by the study.   |         |          |          |                     |
| 10-Shake well to mix   |         |          |          |                     |
| Beyond Use Date: 91 days   |         |          |          |                     |
| Storage: Refrigerate   |         |          |          |                     |
| Reference: Milap C. Nabata, Richard S. Marasco, and Michael T. Brady. Extemporaneous sildenafil citrate oral suspensions for the treatment of pulmonary hypertension in children. American Journal of Health-System Pharmacy, Vol.63, Issue 3, 254-257 |         |          |          |                     |

